### 13.1.2 Change in Rewarding Effects

Change in reported rewarding effects of smoking for cigarettes smoked in the morning, after meals and at other times during the day will be compared.

## 13.2 INTERIM ANALYSIS

An interim analysis will be conducted after results are collected from the first 25 participants, in order to determine whether the trial will stop, or an additional 25 participants will be enrolled, as described above.

# 14 ETHICS AND REGULATIONS

---

## 14.1 IRB APPROVAL

The protocol, informed consent document and relevant supporting information must be submitted to the IRB for review and must be approved before the study is initiated. In addition, any participant recruitment materials must be approved by the IRB prior to being used.

Any change to the protocol must be submitted to the IRB for review and approval before implementation. A protocol change intended to eliminate an apparent immediate hazard to participants may be implemented immediately provided the reviewing IRB are notified within 10 working days.

#### **14.2 INVESTIGATIONAL NEW DRUG APPLICATION**

An Investigational New Drug (IND) application is not required for use of zonisamide or bupropion in this study. This study is not intended to support a new indication, support a change in labeling, support a change in advertising, nor does it involve a change in dosage level or route of administration.

An Investigational New Drug (IND) application is not required for use of Halo G6 in this study because the G6 is not intended for use as a smoking cessation aid.

#### **14.3 INVESTIGATIONAL TOBACCO PRODUCT APPLICATION**

An Investigational Tobacco Product (ITP) application is not required for use of the Halo G6 in this study. The device and the cartomizers were marketed prior to August 8, 2016 and are not being modified for the investigation.

#### **14.4 GCP AND REGULATORY REQUIREMENTS**

This study will be conducted in accordance with the ethical principles that have their origin in the Declaration of Helsinki and that are consistent with Good Clinical Practice and applicable regulatory requirements. The study must be conducted in accordance with the regulations of the United States Food and Drug Administration (FDA) as described in 21 CFR 50 and 56, applicable laws and the IRB requirements.

#### **14.5 PARTICIPANT INFORMATION AND CONSENT**

It is the responsibility of the investigator to provide each participant with full and adequate verbal and written information using the IRB-approved informed consent form (ICF), including the objective and procedures of the study and the possible risks involved before inclusion in the study. Informed consent must be obtained prior to performing any study-related procedures.

The signed and personally dated original and completed ICF(s) must be kept by the Investigator and filed in the Investigator study file at the site or with the participant's files and a copy must be given to the participant. The participant will be informed that if they discontinue from the study, the data collected until the point of discontinuation will be maintained as part of the study data and the samples collected prior to discontinuation will be analyzed, unless they refuse in writing.

#### **14.6 AMENDMENT TO INFORMED CONSENT FORM**

If a protocol amendment is required, an amendment may be required to the ICF. If revision of the ICF is necessary, the Investigator or designee will ensure that the documents have been reviewed and approved by the IRB before participants are informed and sign the amended ICF (including date and time).

## 15 ADMINISTRATIVE CONSIDERATIONS

---

### 15.1 PARTICIPANT CONFIDENTIALITY

All information obtained during the conduct of the study with respect to the participants' state of health will be regarded as confidential. A statement to this effect will be written in the information provided to the participant. An agreement to disclose any such information will be obtained from the participant in writing and signed by the participant, in compliance with all local and national data protection and privacy legislation.

Study records that identify participants will be kept confidential as required by law. Except when required by law, participants will not be identified by name, social security number, address, telephone number, or any other direct personal identifier in study records disclosed outside of Rose Research Center. For records disclosed outside of Rose Research Center, participants will be assigned a unique code number. The key to the code will be kept separate from the locked file where the study records are stored.

### 15.2 RECORD RETENTION

All records of data, in any form, will be maintained by Rose Research Center as required by ICH/GCPs. Essential documents will be retained for at least 15 years after completion of the study.

Appropriate measures will be taken to prevent accidental or premature destruction of these documents.

## Appendix 1 - Patient Health Questionnaire (PHQ-9)

**PATIENT HEALTH QUESTIONNAIRE (PHQ-9)**

Over the last 2 weeks, how often have you been bothered by any of the following problems?

	Not at all	Several days	More than half the days	Nearly every day
1. Little interest or pleasure in doing things				
2. Feeling down, depressed, or hopeless				
3. Trouble falling or staying asleep, or sleeping too much				
4. Feeling tired or having little energy				
5. Poor appetite or overeating				
6. Feeling bad about yourself- or that you are a failure or have let yourself or your family down				
7. Trouble concentrating on things, such as reading the newspaper or watching television				
8. Moving or speaking so slowly that other people could have noticed. Or the opposite- being so fidgety or restless that you have been moving around a lot more than usual				
9. Thoughts that you would be better off dead, or of hurting yourself in some way				

10. If you checked off *any* problems, how *difficult* have these problems made it for you to do your work, take care of things at home, or get along with other people?

- Not difficult at all
- Somewhat difficult
- Very difficult
- Extremely difficult

## Appendix 2 – Fagerström Test for Nicotine Dependence (FTND)

## FAGERSTRÖM TEST FOR NICOTINE DEPENDENCE

INSTRUCTIONS: Please mark the answer that most accurately answers each question.

1. How soon after you wake up do you smoke your first cigarette?

- Within 5 Minutes       6-30 Minutes       31-60 Minutes       After 60 Minutes

2. Did you find it difficult to refrain from smoking in places where it is forbidden, e.g., in church, at the library, in the cinema, etc.?

- Yes  
 No

3. Which cigarette would you hate most to give up?

- The first one in the morning  
 Any other

4. How many cigarettes per day do you smoke?

- 31 or more       21-30       11-20       10 or less

5. Do you smoke more frequently during the first hours of waking than during the rest of the day?

- Yes  
 No

6. Do you smoke if you are so ill that you were in bed most of the day?

- Yes  
 No

Appendix 4 – Smoking History

### SMOKING HISTORY

What brand of cigarettes do you smoke? \_\_\_\_\_

Color of cigarette pack? \_\_\_\_\_

Size:             Kings                       Regulars             72's             100's             120's

Flavor:             Menthol                       Non-menthol

Pack type:         Hard pack                       Soft pack

Filtered?          Filtered                       Unfiltered

1. How many cigarettes do you smoke a day? \_\_\_\_\_cigs per day

2. How old were you when you first smoked a cigarette? \_\_\_\_\_ years old

3. How old were you when you became a regular smoker? \_\_\_\_\_ years old

4. How many years have you been a regular smoker? \_\_\_\_\_ years

Have you been a regular smoker for the past year?

Yes                       No

5. How many times have you tried to seriously quit smoking (for at least 1 day)? \_\_\_\_\_ attempts

6. Since you first started smoking, what was the longest period of time that you were able to stay off cigarettes? (If less than 1 day, do not include time sleeping) \_\_\_\_\_

Hours             Days             Weeks             Months             Years

7. Have you participated in a smoking study in the past?

Yes                       No

If YES, when? \_\_\_\_\_ Where? \_\_\_\_\_

8. Are you interested in switching from a combustible cigarette to an electronic cigarette?

Yes                       No

9. Have you smoked cigar in the past 14 days?

Yes                       No

10. Have you smoked a pipe, hookah or an e-cigarette in the past 14 days?

Yes                       No

11. Have you used snuff or chewing tobacco in the past 14 days?

Yes                       No

Form of ID Verified:  Driver's License  Photo ID  Military ID  Passport					
_____				_____	
Research Personnel's Signature				Date	

Appendix 6 – Medical History Form

### MEDICAL HISTORY FORM

Major Medical Conditions		
Have you ever had or are currently having/ being treated for any of the following conditions?		
 Yes	 No	High blood pressure (Hypertension)
 Yes	 No	Heart attack, Heart Failure, OR heart disease diagnosis by cardiac angiogram
 Yes	 No	Problems with heart valves such as mitral regurgitation, stenosis, artificial valve or other
 Yes	 No	Heart rhythm problem such as atrial fibrillation, tachycardia, or pacemaker
 Yes	 No	Prior surgery on the gastrointestinal tract (e.g. colectomy, gastric by-pass, Reux-En-Y)
 Yes	 No	Skin problems
 Yes	 No	Cirrhosis of the liver
 Yes	 No	Liver problems other than cirrhosis (e.g. Hepatitis, fatty liver)
 Yes	 No	Kidney failure
 Yes	 No	Chronic Kidney Disease
 Yes	 No	Chronic Diarrhea and/or constipation such as Irritable Bowel Syndrome, Crohn's Disease, Inflammatory Bowel
 Yes	 No	Stomach/ Duodenal Ulcer (Gastrointestinal Ulcer)
 Yes	 No	Chronic Bronchitis (cough every morning)
 Yes	 No	Chronic Obstructive Pulmonary Disease (COPD) or Emphysema
 Yes	 No	Other lung disorder such as Tuberculosis, Pulmonary Fibrosis, Sarcoid
 Yes	 No	Asthma
 Yes	 No	Stroke or TIA (mini stroke)
 Yes	 No	Seizure/ epilepsy
 Yes	 No	Migraine headaches
 Yes	 No	Unexplained fainting spells
 Yes	 No	Insomnia
 Yes	 No	Other neurologic conditions
 Yes	 No	Problems giving blood samples
 Yes	 No	Anemia requiring iron
 Yes	 No	Blood disorder
 Yes	 No	Rheumatic Disease such as Rheumatoid Arthritis, Fibromyalgia, other
 Yes	 No	Sinusitis/ Seasonal allergies
 Yes	 No	Other severe allergies
 Yes	 No	Diabetes or Pre-diabetes
 Yes	 No	Thyroid disease or condition
 Yes	 No	Cancer
 Yes	 No	Depression/ Anxiety/ Bipolar disorder
 Yes	 No	Post-traumatic stress disorder
 Yes	 No	Other Psychiatric problems (e.g., Borderline, Schizoaffective, Schizophrenia, Hypomania, ADHD)
 Yes	 No	History of Sexually Transmitted Disease (STD)
 Yes	 No	Chronic infectious syndrome such as HIV, CMV, Epstein Barr
 Yes	 No	History of drug or alcohol abuse
 Yes	 No	Intolerance to medications
 Yes	 No	Other major medical condition

Office use only:

### MEDICAL HISTORY FORM

#### Past Medical History

Please list any illnesses that have caused you to miss work or have interrupted your life this past year:

1.		Mo/Yr:	
2.		Mo/Yr:	
3.		Mo/Yr:	
4.		Mo/Yr:	
5.		Mo/Yr:	

Please list any hospitalizations. If possible, include the year:

1.		Mo/Yr:	
2.		Mo/Yr:	
3.		Mo/Yr:	
4.		Mo/Yr:	
5.		Mo/Yr:	

Please list any serious injuries or accidents. If possible, include the year:

1.		Mo/Yr:	
2.		Mo/Yr:	
3.		Mo/Yr:	
4.		Mo/Yr:	
5.		Mo/Yr:	

Please list any surgeries or major procedures, along with the reason. If possible, include the year:

1.		Mo/Yr:	
2.		Mo/Yr:	
3.		Mo/Yr:	
4.		Mo/Yr:	
5.		Mo/Yr:	

Office use only:

## MEDICAL HISTORY FORM

### Family History

Please mark an "x" for any first-degree family member(s) (children, parents, or siblings) that currently has or had any of the following illnesses (select all that apply):

Illness	Mother	Father	Sister	Brother	Daughter	Son	None
Anemia or Blood disease							
Cancer							
Diabetes							
Glaucoma							
Heart disease							
High blood pressure							
Mental Illness/ Depression/ Generalized Anxiety							
Stroke							
Substance abuse (alcohol, tobacco or other)							
Other serious illness:							

### Social History

Please complete the following questions:

Do you drink alcohol, beer, or wine?  Yes  No If YES, how many drinks per week? \_\_\_\_\_  
 How many drinks do you have on your heaviest drinking day of the week? \_\_\_\_\_

---

Do you drink coffee, tea, caffeinated soda daily?  Yes  No If YES, how many cups per day? \_\_\_\_\_

---

Have you used a non-prescription drug such as marijuana, cocaine, heroin in the last month? Have you used prescription drugs not prescribed to you?  Yes  No If YES, when and what drug/ substance and last date of use: \_\_\_\_\_

---

Have you used an Experimental (investigational) drug or biologic in the past 30 days?  Yes  No

### Blood Donation

Please complete the following question:

Have you donated any blood or blood products within the last 2 months?  Yes  No If YES, what blood product (whole blood, plasma, platelets, etc.)? \_\_\_\_\_

### General Health

Please complete the following questions:

Do you use supplemental oxygen?  Yes  No

---

Can you walk up 2 flights of stairs?  Yes, without stopping  Yes, but I need to stop along the way  No

### MEDICAL HISTORY FORM

#### General Health (continued)

How well do you walk?  Independently  I use a cane or walker  I use a wheelchair

Do you use CPAP machine?  Yes  No

#### General Health (Women Only)

Do you agree to use a medically acceptable form of birth control for the duration of the study?  Yes  No

If yes, please select form of contraception you and/or your partner plan to use or are currently using.

- Tubal ligation / Hysterectomy / Bilateral oophorectomy  Vasectomy
- Birth control pills / patches / implants / injections  Not heterosexually active
- Condom / Diaphragm used with spermicide  None
- Intrauterine device (IUD) / Essure  Post-menopausal

#### Medications

Please list any allergies and the reaction caused by the allergy (e.g. "rash" or "tongue swelling" or "itchiness"):

--	--	--

#### Medications List

Please list all medications you have used within the last month (include over-the counter drugs, vitamins/ supplements, and especially prescriptions):

Name of medication	Dosing (mg/tabs/pills) and Route (oral, topical)	Frequency (times per day)	Start date	Stop date	Prescribed for what problem?

### MEDICAL HISTORY FORM

#### **Smoking Cessation Products**

For each of the following, mark if you have used the product, experienced any side effects, allergy or intolerance with usage or had to stop using the product due to side effects:

	Not Used	Used	Side Effects	Stopped due to Side Effects	
				 Yes	 No
Nicotine Patch				 Yes	 No
Nicotine Gum				 Yes	 No
Nicotine Lozenge				 Yes	 No
Nicotine Inhaler				 Yes	 No
Nicotine Nasal Spray				 Yes	 No
Zyban (wellbutrin)				 Yes	 No
Chantix (varenicline)				 Yes	 No

Have you used any of these products within the past 14 days?       Yes     No

_____ MD/ PA Signature	_____ Date
---------------------------	---------------

## Appendix 7- Review of Systems Form

## REVIEW OF SYSTEMS

Are you currently (in the last 30 days) having/ being treated for any of the following conditions:

**General:** (\_\_\_ none of these apply)

- |  |  |   |
|--|--|---|
|  Unexplained weight loss or gain |  Fever or chills |  Trouble Sleeping |
|  Fatigue/ Lack of energy         |  Weakness        |   |

**Skin:** (\_\_\_ none of these apply)

- |                                 |                                  |  |
|---------------------------------|----------------------------------|--|
|  Rashes |  Itching |  Color changes         |
|  Lumps  |  Dryness |  Hair and nail changes |

**Head:** (\_\_\_ none of these apply)

- |                                   |                                      |
|-----------------------------------|--------------------------------------|
|  Headache |  Head Injury |
|-----------------------------------|--------------------------------------|

**Ears:** (\_\_\_ none of these apply)

- |  |                                  |  |
|--|----------------------------------|--|
|  Decreased hearing |  Earache |  Ringing in ears |
|--|----------------------------------|--|

**Eyes:** (\_\_\_ none of these apply)

- |  |  |                                  |
|--|--|----------------------------------|
|  Vision problems |  Blurry or double vision |  Redness |
|  Specks          |  Flashing lights         |  Pain    |

**Nose:** (\_\_\_ none of these apply)

- |                                     |                                     |                                      |
|-------------------------------------|-------------------------------------|--------------------------------------|
|  Stuffiness |  Itching    |  Nose Bleeds |
|  Discharge  |  Sinus pain |                                      |

**Throat:** (\_\_\_ none of these apply)

- |   |                                      |  |
|---|--------------------------------------|--|
|  Teeth/gum problems |  Sore tongue |  Thrush                |
|  Dentures           |  Dry mouth   |  Non-healing sores     |
|  Hoarseness         |  Sore throat |  Difficulty swallowing |

**Neck:** (\_\_\_ none of these apply)

- |                                    |                               |   |
|------------------------------------|-------------------------------|---|
|  Lumps     |  Pain |  Swollen glands |
|  Stiffness |                               |   |

**Respiratory:** (\_\_\_ none of these apply)

- |   |  |                                   |
|---|--|-----------------------------------|
|  Cough (dry or wet, productive) |  Coughing up blood |  Wheezing |
|  Shortness of breath            |  Painful breathing |                                   |

**Cardiovascular:** (\_\_\_ none of these apply)

- |   |  |   |
|---|--|---|
|  Chest pain or discomfort                 |  Difficulty breathing lying down   |  Suddenly awaking from sleep with shortness of breath |
|  Tightness                                |  Swelling                          |   |
|  Heart pounding/ Fluttering/ Palpitations |  Shortness of breath with activity |   |

**Gastrointestinal:** (\_\_\_ none of these apply)

- |  |   |  |
|--|---|--|
|  Swallowing difficulties |  Change in bowel habits |  Yellow eyes or skin |
|  Heartburn               |  Rectal bleeding        |  Change in appetite  |
|  Constipation            |  Diarrhea               |  Nausea              |
|  Vomiting                |  Stomach pain           |  |

**Urinary:** (\_\_\_ none of these apply)

- |                                    |  |   |
|------------------------------------|--|---|
|  Frequency |  Blood in urine      |  Change in urinary strength |
|  Urgency   |  Pain with urination |  Incontinence               |

### REVIEW OF SYSTEMS

**Vascular:** (     none of these apply)

- Calf pain with walking
- Leg cramping
- Leg pains

**Musculoskeletal:** (     none of these apply)

- Muscle or joint pain
- Back pain
- Swelling of joints
- Stiffness
- Redness of joints
- Trauma

**Neurologic:** (     none of these apply)

- Dizziness
- Weakness
- Tremor
- Fainting
- Numbness
- Shaking episodes
- Tingling

**Hematologic:** (     none of these apply)

- Bruise easily
- Bleed easily

**Endocrine:** (     none of these apply)

- Heat or cold intolerance
- Frequent urination
- Change in appetite
- Sweating
- Thirst

**Psychiatric:** (     none of these apply)

- Nervousness
- Memory loss
- Feeling down

**Females only:** (     none of these apply)

- Pregnant or currently breast feeding

Office Use Only

\_\_\_\_\_  
MD/ PA Signature

\_\_\_\_\_  
Date

## Appendix 8 – Employment History

**EMPLOYMENT HISTORY**

1. What is the highest degree you have completed?

- High school diploma or G.E.D.
- Technical degree
- Two year associates degree (e.g. A.A.)
- Four year undergraduate degree (e.g. B.A., B.S.)
- Professional degree (e.g. P.A., R.N.)
- Master's degree (e.g. M.A., M.S., M.B.A.)
- Doctorate (e.g. Ph. D., M.D., J.D.)
- Other \_\_\_\_\_

2. How many years of formal education have you completed: (Include grade school and higher) \_\_\_\_\_

3. What is your current employment status?

- Not employed (please answer question 4)
- Part-Time work
- Full-time work

4. If not employed is selected, please specify your answer:

- Education (Full-time student)
- Retired
- Medical leave
- Homemaker
- Laid off
- Other \_\_\_\_\_

5. What is your current job title; if no longer employed, in what position were you last employed?

---

6. How physically demanding is your current employment?

- Not employed
- Not demanding at all
- Very little demanding
- A little demanding
- Somewhat demanding
- Moderately demanding
- Very demanding
- Extremely demanding

7. How mentally or emotionally stressful is your current employment?

- Not employed
- Not stressful at all
- Very little stress
- A little stressful
- Somewhat stressful
- Moderately stressful
- Very stressful
- Extremely stressful

8. What is your gross (before taxes) annual household income?

- < \$16,000
- \$16,001- \$32,000
- \$32,001- \$48,000
- \$48,001- \$64,000
- \$64,001- \$80,000
- \$80,001- \$96,000
- >\$96,000

9. What are your estimated total assets? (Include house, automobiles, stocks, savings, furniture, etc.).

- <\$50,000
- \$50,001- \$100,000
- \$100,001- \$200,000
- \$200,001- \$300,000
- \$300,001- \$400,000
- \$400,001- \$500,000
- \$500,001- \$750,000
- >\$750,001

10. How many people live in your household? \_\_\_\_\_

Appendix 9 – modified Cigarette Evaluation Questionnaire - Ext (mCEQ-E)

### CIGARETTE EVALUATION QUESTIONNAIRE- Ext modified

Have you smoked any cigarettes since your last visit?

- No: Skip questionnaire
- Yes: Please answer the following questions based on the **FIRST** cigarette you smoked on the last day you smoked.

	Not at all	Very little	A little	Moderately	A lot	Quite a lot	Extremely
1. Was it satisfying?							
2. Did it taste good?							
3. Did it make you dizzy?							
4. Did it calm you down?							
5. Did it help you concentrate?							
6. Did it make you feel more awake?							
7. Did it reduce your hunger for food?							
8. Did it make you nauseated?							
9. Did it make you feel less irritable?							
10. Did you enjoy the sensations of the smoke in your throat and chest?							
11. Did it immediately reduce your craving for cigarettes?							
12. Did you enjoy smoking?							

Please answer the following questions based on the cigarette smoked **immediately after a meal**.

- Did not smoke **immediately after a meal**: Skip section

	Not at all	Very little	A little	Moderately	A lot	Quite a lot	Extremely
1. Was it satisfying?							
2. Did it taste good?							
3. Did it make you dizzy?							
4. Did it calm you down?							
5. Did it help you concentrate?							
6. Did it make you feel more awake?							
7. Did it reduce your hunger for food?							
8. Did it make you feel nauseated?							
9. Did it make you feel less irritable?							

10. Did you enjoy the sensations of the smoke in your throat and chest?							
11. Did it immediately reduce your craving for cigarettes?							
12. Did you enjoy smoking?							

Please answer the following questions regarding **all other cigarettes smoked** on the last day you smoked.

	Not at all	Very little	A little	Moderately	A lot	Quite a lot	Extremely
1. Was it satisfying?							
2. Did it taste good?							
3. Did it make you dizzy?							
4. Did it calm you down?							
5. Did it help you concentrate?							
6. Did it make you feel more awake?							
7. Did it reduce your hunger for food?							
8. Did it make you nauseated?							
9. Did it make you feel less irritable?							
10. Did you enjoy the sensations of the smoke in your throat and chest?							
11. Did it immediately reduce your craving for cigarettes?							
12. Did you enjoy smoking?							

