### 2.3 CHANGE IN REWARDING EFFECTS OF SMOKING CIGARETTES

Secondary analyses will evaluate the hypothesis that enjoyment of smoking after meals is attenuated by zonisamide/bupropion treatment. The smoking satisfaction scale of the mCEQ-E will be compared between cigarettes smoked after meals versus all others smoked during the day, examining how this difference changes after zonisamide/bupropion usage. Additionally, the proportion of participants who report smoking after meals, while reporting not smoking at other times, will be compared between the first week and the weeks after zonisamide/bupropion usage.

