#### 8.2.14.2 ***Modified Cigarette Evaluation Questionnaire-Extended (mCEQ-E) and Modified Electronic Cigarette Evaluation Questionnaire-Extended (mECEQ-E)***

The Cigarette Evaluation Questionnaire was initially developed in the PI's laboratory and used in numerous studies to assess the effects of pharmacological treatments on the rewarding effects of cigarette smoking. The mCEQ-E will be utilized to assess the degree to which participants experience the reinforcing of smoking, providing five subscale scores: smoking satisfaction (satisfying, tastes good, enjoy smoking), psychological rewards (calms down, more awake, less irritable, helps concentrate, reduces hunger), aversion (dizziness, nauseated), enjoyment of respiratory tract sensations (single-item assessment), craving reduction (single-item assessment). Participants will be asked to assess the 12 items of the questionnaire on a 7-point scale, ranging from "not at all" to "extremely". These 12 items will be asked for the "first cigarette smoked", "cigarette immediately after a meal", and "all other cigarettes." The e-cigarette version of this questionnaire (mECEQ-E) will also be used.

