## 8.6 SMS MESSAGING

8.6.1 Daily SMS Message (after screening, prior to V2) – Participants will receive a text with a link to a survey to access the following:

- Have you smoked any combustible cigarettes today?
  - If yes, how many cigarettes did you smoke?
  - What was your favorite cigarette of the day?  
1-First one, 2-One immediately after a meal, 3-Any other cigarette

8.6.2 Daily SMS Message (From Visit 2) -- Participants will receive a text with a link to a survey to assess the following:

- Have you smoked any combustible cigarettes today?
  - If yes, how many cigarettes did you smoke?
  - Which cigarette did you smoke today? (If only 1 cigarette is reported)  
1-First one of the day, 2-One immediately after a meal, 3-Any other cigarette
  - What was your favorite cigarette of the day? (Of more than 1 cigarette is reported)  
1-First one, 2-One immediately after a meal, 3-Any other cigarette
- Have you used your e-cigarette today?
  - If yes, how many times did you use your e-cigarette today?
- Did you take your study drugs this morning? (After Visit 3)

8.6.3 6-Month follow up SMS Message -- Participants will receive a text with a link to a survey to assess the following:

- Have you smoked a combustible cigarette since your last visit?
  - If yes, are you still smoking combustible cigarettes right now?
  - How many combustible cigarettes do you smoke per day on average?
- Have you used an e-cigarette since your last visit?
  - If yes, are you still using an e-cigarette?
  - How often do you use an e-cigarette?
- Have you used any other nicotine containing products (other than e-cigarettes) since you last visit?

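### The mCEQ-E block on all other cigarettes has no none-smoked exit, so the after-meal satisfaction contrast can be distorted when only first or after-meal cigarettes were smoked

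*Combined protocol and SAP*

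**What the plan says.** Appendix 9 asks about three occasions: the first cigarette of the last smoking day, the cigarette immediately after a meal, and all the rest. A gate at the top, "Have you smoked any cigarettes since your last visit", skips the whole form only for people who have not smoked at all since the previous visit. The after-meal block has its own exit: "Did not smoke immediately after a meal: Skip section". The third block has none. Its instruction, "Please answer the following questions regarding all other cigarettes smoked on the last day you smoked", is followed directly by the grid. Section 8.2.14.2 describes the response format ("Participants will be asked to assess the 12 items of the questionnaire on a 7-point scale") and gives no not-applicable option. Appendix 10, the e-cigarette version, has the same layout.

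The third block feeds a planned secondary analysis. Section 2.3 states: "The smoking satisfaction scale of the mCEQ-E will be compared between cigarettes smoked after meals versus all others smoked during the day", and then looks at how this difference changes with treatment. Section 13.1.2 describes a three-way comparison: "cigarettes smoked in the morning, after meals and at other times during the day will be compared".

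The protocol itself expects days on which the third category is empty. Section 2.3 plans to track "the proportion of participants who report smoking after meals, while reporting not smoking at other times", and the daily text in Section 8.6.2 has a branch for single-cigarette days: "Which cigarette did you smoke today? (If only 1 cigarette is reported". No scoring or missing-data rule covers an empty third block.

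**The concern.** The form allows for one category being empty (after meals) but not for the other that can be empty (all the rest). The unhandled case is close to the study's own hypothesis. Section 1.2 proposes that the cigarettes hardest to give up are the ones after meals, so a participant who has cut down to only those is someone the protocol expects to see. That participant reaches a page asking for 12 ratings of cigarettes that were not smoked.

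At stake is the satisfaction contrast, the protocol's stated test of whether the drug combination weakens enjoyment of the after-meal cigarette. Entrants smoke at least 10 a day (Section 4.1.1), so an empty third category should be rare at V2 and more common as smoking falls. An artefact that grows over visits can be read as change over time, and a single-group study (Section 3.1) has no control arm to show otherwise.

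**Working it through.** The documents give no sample size, power or expected value for this contrast, so there is no figure to reproduce. The check is a comparison of cases, followed by an illustration on assumed values.

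**Cases.** Write D = S_meal − S_other, where S_meal is satisfaction from the after-meal block and S_other is satisfaction from the third block. The after-meal instruction names no day; I read it as the same last smoking day as the other two blocks.

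| Cigarettes on the rated day | After-meal block | Third block | D |
|---|---|---|---|
| One, not after a meal | Exit ticked | No referent | Missing, whatever is entered |
| One, after a meal | Rates the same cigarette as the first block | No referent | Missing if blank, artefact if filled |
| Only first and after-meal cigarettes | Rated | No referent | Missing if blank, artefact if filled |
| After-meal and other cigarettes | Rated | Rated | Valid |

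The problem therefore arises in the second and third rows only. It is not the same as a one-cigarette day: the first row is harmless, and the third row involves two or more cigarettes.

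The third row also depends on a point left open. Section 2.3 does not say whether the first cigarette belongs among all others, while Section 13.1.2 lists morning cigarettes separately. If it does belong, the first-cigarette block could supply a comparator in the third row, but in the second row the same cigarette would sit on both sides of the contrast.

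**Illustration.** These inputs are all assumptions:
- items coded 1 to 7 (the coding is not stated);
- S_meal = 4;
- a true mean contrast D0 = 1 in the valid forms;
- a share f of the *computed* contrasts coming from filled-in empty blocks.

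An empty block gives d = 4 − 1 = +3 if the lowest option is marked, 4 − 4 = 0 if the after-meal answers are copied, and 4 − 7 = −3 if the highest option is marked. The observed mean is (1 − f) × D0 + f × d, so the shift is f × (d − D0).

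| f | Lowest marked (d = +3) | Copied (d = 0) | Highest marked (d = −3) |
|---|---|---|---|
| 10% | 0.9 + 0.3 = 1.2 | 0.9 + 0 = 0.9 | 0.9 − 0.3 = 0.6 |
| 25% | 0.75 + 0.75 = 1.5 | 0.75 + 0 = 0.75 | 0.75 − 0.75 = 0.0 |
| 50% | 0.5 + 1.5 = 2.0 | 0.5 + 0 = 0.5 | 0.5 − 1.5 = −1.0 |

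With S_meal = 2 the three values of d are +1, 0 and −5; with S_meal = 6 they are +5, 0 and −1. The result also depends on D0. At f = 25% and S_meal = 4, marking the lowest option shifts the mean by 0.25 × (3 − 1) = 0.5 if D0 = 1, and by 0.25 × (3 − 0) = 0.75 if D0 = 0. Copying shifts it by 0.25 × (0 − 1) = −0.25 if D0 = 1, and not at all if D0 = 0. The sign depends on how people respond, which the documents do not tell us.

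**The case against.** The strongest reply is that this is a gap in form wording that may do no harm. Nothing makes an answer compulsory: Section 8.2.14 allows paper or electronic forms, and Section 12.1 refers missing or unclear data to the investigator. A sensible participant may leave the block blank, and the contrast is then simply missing. The analysis is secondary, in a pilot of 25 to 50 people.

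Much of that stands, and it rules out several stronger statements that a reader might infer:

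- *That participants will rate cigarettes that do not exist.* They may; the form invites it but does not force it. A blank is not harmless either, because without an exit it cannot be told from a section missed by accident.
- *That the false values fall only on the post-drug side.* The e-cigarette is supplied at V2 and the drugs start a week later at V3 (Section 3.1). The mCEQ-E is scheduled at both visits (Section 8.5), so smoking may already be lower at V3 before any drug is taken. Section 2.3 does not name V2 as the baseline for the satisfaction contrast.
- *That the bias runs for, or against, the hypothesis.* The illustration gives both signs.
- *That the mean shifts by f × (S_meal − 1).* That holds only if the lowest option is always marked and the true contrast is zero. Zero sits badly with the premise that after-meal cigarettes are the favorites. The share f must also be taken over computable contrasts, not over everyone who had no other cigarette that day.

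**Conclusion.** The point holds in a limited form. The third block lacks an exit that the after-meal block has. When the rated day held an after-meal cigarette and no other, the third block yields either ratings without a referent or an unexplained blank, and no stated rule deals with either. The Section 2.3 contrast can be distorted as a result, and the distortion can be mistaken for change over time because the case should become more common as smoking falls. That last step is an expectation drawn from the entry criterion, not a figure in the plan.

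Neither the size nor the direction can be derived: the documents give no share of affected forms, item coding, expected contrast or response pattern, and the values shown above are illustrative only. The primary switching outcome and the 16/25 and 28/50 decision rules do not use this questionnaire and are unaffected.

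**What to change.** 1. In Appendix 9, add a line at the head of the third block: *Did not smoke any other cigarettes that day: Skip section*. Add the matching exit to Appendix 10. The second change is for consistency only, since the comparisons in Sections 2.3 and 13.1.2 concern cigarettes.
2. In Section 2.3, state that the contrast is computed only at visits where an after-meal cigarette and a separate other cigarette were both smoked on the rated day. The same sentence should say whether the first cigarette counts among the others.
3. For forms already completed, set the contrast to missing where the daily text for the rated day reports one cigarette. This catches only some affected forms. It needs a reply for that day, and it misses days with only first and after-meal cigarettes, because with more than one cigarette the text asks only for the favorite.

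The cost is one tick-box on each of two forms and a sentence in the protocol. Slightly fewer contrasts will be computable, but those lost carry no information about after-meal against other cigarettes.
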